Study Protocol

The Assessment and management of Obesity
and Self-maintenance (AMOS) Clinic:
Implementation and Evaluation of the AMOS
Model of Care

Version 7

[figure not shown]

Table of Contents

Title	2
Summary	2
Researchers/Investigators	2
Rationale and Background	3
Study Goals and Objectives	5
Aim.....	5
Objectives.....	5
Outcomes	5
Study Design	7
Rationale for Study Design	8
Methodology	8
Randomisation.....	8
Study Intervention.....	9
Clarification of Intervention.....	9
Usual Care Contextualised to the Rural Setting.....	11
Management of Cross Contamination.....	12
Orlistat and other Weight Medications.....	12
Orlistat as the Pharmaceutical Intervention & Bariatric Surgery.....	13
Flow Chart.....	14
Study Duration/Timelines	15
Study Population	15
Participants Inclusion/Exclusion Criteria	15
Lay Description of Participation.....	15
Nature of Existing Relationships and Voluntary Consent.....	16
Impact of Research on Participant/Researcher Relationship.....	16
Male to Female Ratio.....	16
Consideration for Vulnerable Groups.....	16
Data Management and Statistical Analysis	16
Data Management.....	16
Statistical Analysis.....	17
Justification of Effect Size.....	18
Expected Outcomes of the Study	21
Informed Consent	21
Advertisement of Study.....	21
Exposure of Person to Disadvantage or Risk.....	22
Seeking Consent.....	22
Confidentiality and Privacy.....	22
Safety Considerations	23
Expected Benefits to the Wider Community.....	23
Expected Benefits to Participants.....	23
Risk of Harm.....	23
Mechanisms to Monitor the Project.....	24
Data and Safety Monitoring.....	24
Resources	24
Other Personnel Relevant to Research Project.....	24
Training.....	25
Project Funding.....	25
Project Management	26
Prior Reviews	31
Dissemination of Results and Publication	31
References	32

Study Protocol

Title

The Assessment and Management of Obesity and Self-Maintenance (AMOS) Clinic: Implementation and Evaluation of the AMOS Model of Care

Summary

The aim of this project is to assess the effectiveness of an integrated model of obesity care for adult patients with diabetes who also have obesity. The research design is a randomised controlled clinical trial. The project will recruit 212 patients with diabetes and randomise them to active intervention or usual care. The active intervention group will receive an integrated, multidisciplinary model of care for obesity management.

Researchers/Investigators

Principal Investigators

A number of patients attending Diabetes Clinics within Tasmania with excessive BMIs > 40 suffer from significant insulin resistance that is not responsive to any form of oral and/or injectable treatment (Diabetes Centre, 2014). The current BMI of patients attending the Adult Diabetes Clinics in the THO-North West is high; maximum BMI is > 70 and mean 44.5 (Diabetes Centre, 2014). Thus, this population is at particularly high risk of development of additional comorbidities as the mean BMI falls within the Obesity III classification (NHMRC, 2013; AIHW, 2011). Good clinical management underpins what is termed “tertiary prevention”, that is, the prevention of complications arising from established conditions (such as type 2 diabetes); the system of national health financing now in place provides significant financial incentive for increased “efficient” acute activity (Population Health, 2013). In addition, hospitalisation rates in Tasmania are increasing for diabetes and arthritis/musculoskeletal conditions (Population Health, 2013). The north west of Tasmanian holds a higher prevalence of diabetes in the 30 – 39 year old age group (Diabetes Australia, 2014) that identifies a longer duration of potential diabetes and diabetes during maternal child bearing years; pre-pregnancy overweightness and obesity closely associated to adverse obstetric outcomes (Nankervis et al., 2013).

The NHMRC Clinical Practice Guidelines for the Management of Overweight and Obesity in Adults, Adolescents and Children in Australia (2013) (“the Guidelines”) make recommendations regarding the management of individuals who have a body mass index (BMI) greater than 25.0 kg/m² and are at

risk or currently have an obesity related comorbidity. According to these guidelines weight management in adults with overweight and obesity involves multicomponent approaches that incorporate lifestyle management (nutrition, physical activity and psychological interventions), medication management and bariatric surgery in the subgroup of patients in whom these procedures are indicated (NHMRC, 2013).

The development of the national guidelines was underpinned by a comprehensive systematic review of the literature (conducted by [name]). This literature review identified important evidence gaps in the management of patients with diabetes mellitus who also have obesity (NHMRC, 2013). A number of these evidence gaps are the focus of this project.

The multidisciplinary management of patients with obesity and type 2 diabetes is not straightforward. Although national diabetes guidelines recommend the use of laparoscopic banding procedures for patients with obesity who also have type 2 diabetes, the studies upon which this recommendation is based were conducted in patients with type 2 diabetes who had been diagnosed within 2 years of the laparoscopic procedure being performed (NHMRC, 2013). Evidence of effectiveness of surgery from randomised controlled trials in patients with type 2 diabetes of more than 2 years duration is not available.

Health problems related to excess weight impose substantial economic burdens on individuals, families and communities (Tanamas et al., 2013; Colagiuri, 2010). Data from the AusDiab study indicate that the total direct cost for overweight and obesity in 2005 was \$21 billion (\$6.5 billion for overweight and \$14.5 billion for obesity) (Tanamas et al., 2013; Colagiuri 2010). The same study estimated indirect costs of \$35.6 billion per year, resulting in an overall total annual cost of \$56.6 billion. A 1% absolute reduction in mean A1C levels has been associated with a 37% decrease in the risk of microvascular complications and a 21% reduction in the risk of any diabetes-related complication or death (UKPDS, 1998). Further, the 'legacy effect' providing long lasting effect; for all-cause mortality, the hazard ratio was 1 for years 0 to 10, but the risk reduction increased to 21% at year 15 and to 24.7% at year 20 (Livingstone & Fisher, 2007). Reduction in systolic blood pressure by 10mmHg also supporting reduction in end points related to diabetes and risk of death (Livingstone & Fisher, 2007; UKPDS, 1998).

The multidisciplinary management of patients with type 2 diabetes and obesity in rural and remote areas is not straightforward. Although national guidelines recommend multidisciplinary care, the availability of dietitian, psychologist and exercise physiologist supports in rural areas is limited. Further, the effectiveness of multidisciplinary management in rural areas has not been assessed. This is an important evidence gap as the built environment within which lifestyle modification must occur in rural areas is different to the environment within urban areas.

Finally, the systematic review of the literature performed for the development of the national guidelines reveals a lack of evidence for chronic disease models of obesity care rather than models of care that focus on weight loss as the main goal of care (NHMRC, 2013). Chronic disease models of care are of particular relevance to patients with obesity and type 2 diabetes as the likelihood of sustained weight loss in this patient group, even with surgical intervention, has been shown to be low (NHMRC 2013; National Institute for Health and Care Excellence, 2013). It is therefore essential that the secondary complications of obesity (sleep apnoea, hypercholesterolaemia, hypertension, malignancy, infertility, non-alcoholic steatohepatitis, osteoarthritis) (ADIPS 2013; National Cancer Institute 2013; NHMRC, 2013) are identified early and managed effectively in these patients as sustained weight loss is unlikely in spite of weight reduction therapies (NHMRC 2013; National Institute for Health and Care Excellence, 2013).

Study Goals and Objectives

AIM

The aim of this study is to assess the feasibility, acceptability and effectiveness of a rural, multidisciplinary team-based approach to care for adult patients with diabetes mellitus and obesity.

OBJECTIVES OF THIS PROJECT

- To determine if a multidisciplinary multi-intervention clinic for obesity tailored to the individual can reduce absolute cardiovascular and morbidity risk
- To evaluate management and treatment factors as potential predictors of outcome
- To determine whether an interdisciplinary multi-intervention obesity clinic for people with diabetes improves metabolic profile
- To provide process and impact outcomes to substantiate and drive clinical and policy change supportive of a multidisciplinary systematic approach for patients living with obesity

OUTCOMES

Primary Outcome:	change in HbA1c (measured as a continuous variable) in the intervention group compared with the control group
Timepoint:	at 6, 12, 18 and 24 months post baseline; also 6 and 12 months post intervention
Primary Outcome:	change in body weight (measured as a continuous variable) in the intervention group compared with the control group
Timepoint:	at 12 and 24 months post baseline; also 6 and 12 months post intervention
Secondary Outcome:	a decline in Edmonton Obesity status
Timepoint:	at 12 and 24 months post baseline, and 12 months post intervention
Secondary Outcome:	change in absolute cardiovascular risk
Timepoint:	at 12 and 24 months post baseline, and 12 months post intervention
Secondary Outcome:	proportion of participants achieving individualised HbA1c targets according to the Australian Diabetes Society guidelines
Timepoint:	at 12 and 24 months post baseline; also 12 months post intervention
Secondary Outcome:	impact on psychometric scores as assessed using the Assessment of Quality of Life (SF-36), Patient Health Questionnaire (PHQ-9) [Depression] and Generalised Anxiety Disorder Assessment (GAD-7) [Anxiety], Assessment of Quality of Life (AQoL), Work Productivity and Activity Impairment (WPAI)
Timepoint:	at 6, 12, 18 and 24 months post baseline; also 6 and 12 months post intervention

Outcome measures and collection time points							
Measure	Base line	6 mth	12 mth	18 mth	24 mth	6 mth POST	12mth POST
Demographic and clinical measures:							
Demographic data, duration of diabetes	X						

 Demographic data, duration of diabetes at baseline only – to ensure similar characteristics of both the intervention and control groups. 							
Biometric measures; weight, BMI, girth, BP	X	X	X	X	X	X	X

 To review changes in metabolic parameters Time points to allow for intensification of treatment as deemed required Based on evidenced based guidelines/ peer-reviewed literature for timely treatment 							
Co-morbidities, medications	X		X		X		X

 To review changes (improvement/deterioration) in other co-morbidities as a result of treatment for obesity Review interval increased as changes in medication and disease profiles require review time, further based on timelines for review and assessment in peer-reviewed literature. 							
Edmonton obesity staging	X		X		X		X

 The Edmonton obesity staging system independently predicted increased mortality even after adjustment for contemporary methods of classifying adiposity (Padwal et al., 2011). The Edmonton obesity staging system may offer improved clinical utility in assessing obesity-related risk and prioritizing treatment. The project is targeting gradual weight loss that is linked to sustained weight loss – thus timing for assessment are linked to overall weight loss and potential co-morbidity reduction as estimated in peer reviewed literature 							
Sleepiness Scale	X		X		X		X

 Sleep apnoea is independently linked to insulin resistance Time points related to practical timeline for referral, review, assessment and treatment of any diagnosed sleep disturbance 							
McCaffery Pain assessment scale/ Physical function	X	X	X	X	X		X

 Pain is a common symptoms of patients attending the service with obesity and little is generally done for chronic pain in Tasmania – as a result the patient is not able to undertake the physical activity recommendations provided to them Time points for assessment are related to timelines of psychometric scales as these results are closely related and can vary at differing points. Further, as identified in other peer literature 							
Metabolic markers							
Absolute CVD risk	X		X		X		X
HbA1c, Lipids, eGFR LFTs	X	X	X	X	X	X	X
Leptin, ketone, ACR vitamin D, B12, TFTs	X		X		X		X

 The metabolic markers listed above were chosen as they are generally those reported on in other studies, they provide indication of metabolic profile and the need to intensify treatment and/or provide treatment for a deficiency that is related to reduction of metabolism Time intervals chosen are related to evidence based screening timelines supported by peer-reviewed literature NB: Ketone and leptin will not be screened in the post intervention data 							

Measure	Base line	6 mth	12 mth	18 mth	24 mth	6 mth POST	12mth POST
Psychometric measures							
PHQ-9 [Depression] and GAD-7 [Anxiety]	X	X	X	X	X	X	X
SF-36 Quality of Life scaling	X	X	X	X	X	X	X
Assessment of Quality of Life (AQOL)	X	X	X	X	X	X	X
Work Productivity and Activity Impairment	X	X	X	X	X	X	X

TSRAC QUESTION 8 (Response)
 
 Initially the decision was made to use the K10 as a brief measure of psychological distress. This was intended to act as a “triage” for psychological support grouping. Initially the discussions agreed that this was the best option in terms of being conservative in the amount of time being requested of participants. However, the K10 is more a population measure (with norms) rather than used to compare specific research populations. The DASS scale is not being utilised within this research study The PHQ-9 (depression) and GAD-7 (Anxiety) have been chosen as they are validated tools widely used in other research that has focused on the issues of diabetes or obesity, such as the MILES study. The PHQ and GAD are based on the DSM-IV diagnostic criteria. The SF-36 is a generic measure of quality of life. There are a number of other options, however many of them are diabetes specific (or focus on another specific health condition). Given the AMOS project is potentially going to be rolled out to those without diabetes, a more generic measure is more appropriate. It is widely used, acceptable reliability and validity, and norms are available for a range of clinical and nonclinical populations. Time points for assessment and review have been chosen due to fluctuating nature of these measurements and as used in other peer reviewed literature 							
Health professional referral measures							
Referral to other health professionals	X		X		X		
Psychology review	X		X		X		
Physiotherapy review*	X		X		X		
Dietitian review #	X		X		X		
Group training (Stanford – GTMOL)	X		X		X		

 Referral points to AHPs and group program were chosen as outcome measures as a variable that has altered care or treatment Time points for this collection was selected due to presumed referral in line with study protocol. 							

Study Design TSRAC v2 Q1

- Parallel randomised waitlist control trial conducted in the Diabetes Centre of the THO-North West; individuals wait listed for the obesity clinic (*the experimental intervention*) becomes the control group.
- Participants who fit the inclusion criteria will be recruited from pre-existing clinics and listed in order of BMI – subsequently randomly assigned to the two arms of the study via use of an Excel Random Number Generator.
- Recruitment will start initially with the first 106 identified through the excel program for the two groups and will continue until 106 participants have been recruited into both arms.

Rationale for Study Design TSRAC QUESTION 1 (Response)

- According to the NHMRC levels of evidence, a RCT is level 2 evidence and a systematic review of RCTs is level 1 evidence. Program evaluation is not a research method. Rather, program evaluation is conducted using a range of different research methods that are adapted to the task of evaluation depending on the program and the circumstances of its implementation. As this study is an intervention study that examines the effectiveness of an obesity model of care in patients with type 2 diabetes, the higher level of evidence is a RCT and is the study design that the research team wishes to use.
- Initially, all patients will be provided with quality evidenced based care at all times for diabetes and obesity; this form of care for both groups will not alter.
- The potential difficulty for team members to provide services differently depending on whether a client is in the control or intervention group has been addressed by separating participants from the control and intervention group into different clinics. The control group will be seen in the usual diabetes clinic with no particular focus on obesity management and/or the many factors that impact on obesity.
- At differing times a patient in the control group may have an assessment taken ie DASS due to an issue isolated in the course of the clinic however; this is not common but will be accounted for post-hoc in our data analysis.
- The intervention group will have onsite on the day of the clinic a more extensive multidisciplinary team that will be involved in assessment and treatment; unlike the control group clinic.
- Services and treatment will differ due to these assessments and measurement of other markers eg psychometric and pain scales that will prompt differing care and treatment plans.

Methodology

TSRAC QUESTION 2 and 3 (Response)

Randomisation

- All patients referred to the Diabetes Centre are listed in the services clinical software program DiaBASE.
- The list of potential participants was drawn from this program (that is inclusive of all patients as at 10/9/2014)
- Once those that met the exclusion criteria were removed this list of potential participants (359) has been ranked from highest to lowest – at this stage they have been allocated a study number of 1 to 359, 1 being the participant with the highest BMI and 359 with the lowest.
- Numbers have been assigned for the two arms of the study from the computer random number generated via excel.
- According to numbers allocated to the potential participant list these are then assigned to the two arms of the study (intervention and control).
- This will occur once ethic approval has been gained and prior to allocation to clinics
- Once case identified and consent gained participants will be recruited from pre-existing clinics
- Outcome measures will be collected at baseline and at appropriate intervals at 6, 12, 18 months and post intervention at 12 and 24 months.

Study Intervention

- Outcome measures including quantitative and qualitative data **not** usually collected as part of a diabetes clinic will be collected to support the development of individualised plans of care:
 - Absolute cardiovascular disease risk

- Patient Health Questionnaire (PHQ-9) [Depression] and Generalised Anxiety Disorder Assessment (GAD-7) [Anxiety] and SF-36 Quality of Life scaling, Assessment and Quality of Life (AQoL), Work Productivity and Activity Impairment (WPAI)
- McCaffery Pain assessment scale and Physical function status
- Edmonton obesity staging
- Sleepiness Scale
- Metabolic clinical markers (HbA1c, lipids, leptin, ketone, vitamin D, B12, TFTs, LFTs, ACR, eGFR)
- Physical measurements (eg BMI, girth, blood pressure)
- Assessment is undertaken initially on the same day by the physiotherapist in terms of pain management and ability to increase physical activity – these assessments are provided to the endocrinologist and Dietitian at which time a treatment plan is developed in partnership with the client by the multidisciplinary team including:
 - Referral to other health professionals and/or assessments (eg Snore Aust, pain clinic)
 - According to scores from psychometric, physical functioning and/or pain scales participants will be divided into groups A, B or C and referred on for either a once off individual consultation, a series of individual consultations or a group program with relevant AHP.
 - Regular psychology review for CBT and other relevant therapies (according to PHQ-9 and GAD-7)
 - Resistance and hydrotherapy training
 - Medical nutritional therapy
- Following 3 months of lifestyle modification and intensive therapy if weight loss <5% Olistat will be introduced
- At 6 months participants will be referred to self-management program for ongoing behaviour modification
- For relevant cases at 12 months if weight loss not <5% and pathology demonstrates ketosis referral for surgical review
- Bariatric surgical assessment and patient counselling will be provided to determine:
 - whether surgery is indicated;
 - the patient's desire for, and likely tolerance to surgery; and
 - if so, what surgery type is most appropriate for the patient (Nguyen, 2013).

Following the completion of the up to 24 month program (the intervention) participants (both intervention and control) will be invited to continue to be part of the research project by way of providing follow-up data to determine sustainability of the intervention and project. Given Participants are existing patients of the service and will continue to be review as part of routine care at the Diabetes Centre, at their 24 month collection point (intervention and control) participants will be invited to continue with a collection of indicated markers at 6 and 12 months post intervention. If at their last visit (24 months) the participant indicates that they are happy for this to occur this verbal consent will be recorded on the spreadsheet used to collect project data – ie consent given: yes and date. If consent is provided by the participant, ongoing data will be collected following intervention period at 6 and 12 months post intervention.

Intervention Clarified/Differences in two arms of Study TSRAC QUESTION 12 (Response)

- Intervention of interest – **individualised** multidisciplinary multi-intervention assessment and treatment
- The impact of a model of care that assesses, triages and treats **all** factors impacting on metabolic processes from point of entry

Differences in two arms	
Control Group	Intervention Group

 1. Patient attends Diabetes Clinic 2. Pre-assessment includes physical measurements (BMI, BP) and HbA1c by CDE. Plus; Psychological Distress PHQ-9 and GAD-7, QoL SF-36v2, Assessment of Quality of Life (AQoL) and Work Productivity and Activity Impairment (WPAI). The above data will be collected by a research assistant and not the clinicians to prevent impact of 'treatment as usual'. 3. Patient reviewed by endocrinologist and management is diabetes and endocrine focused 4. Screening may include HbA1c, lipids, vitamin B12 and folates, TFTs, LFTs, ACR, eGFR 5. Referral to diabetes educator as needed for ongoing education if HbA1c above target 6. Referral to psychologist as required if patient raises psychosocial problems during consultations with either CDE or endocrinologist 7. Referral to dietitian if HbA1c > 9% in type 2 diabetes 8. Adhoc referral for bariatric assessment if BMI >40 and failed attempts at weight loss 	
 1. Patient attends AMOS Clinic 2. (a) Pre-assessment includes physical measurements (BMI, BP, girth) and HbA1c by CDE. (b) Universal screening - completion of scales to support planned assessment and care: 
 • Psychometric (Psychological Distress PHQ-9 and GAD-7, QoL SF-36v2 and AQoL, WPAI) • Epworth Sleepiness Scale • Absolute cardiovascular risk • Edmonton Obesity Staging (c) Review with physiotherapist for: 
 • Assessment for physical functioning performed • Completion of McCaffery Pain Assessment scale 3. (a) According to psychometric scales patient is triaged into psychologist for 1:1 or group session (b) Patient booked into physiotherapist for 1:1 or group sessions (c) According to dietitian assessment patient seen 1:1 or booked into group program (program facilitated by psychologist and dietitian with focus on identification of barriers) 4. Patient reviewed by endocrinologist and management is diabetes/endocrine and obesity focused 5. Screening for metabolic pathology request provided as per control group with addition of leptin and ketones (to identify weight loss and ketosis) and vitamin D In addition, assessment and review by dietitian to support development of treatment plan. 6. Treatment Plan agreed: 
 • Weight Loss goals determined • Referral as relevant to: 
 ○ Other health professional/specialist (sleep apnoea or pain management assessment if applicable) ○ Community Based Weight /Pain management programs (Stanford - GTMOL, OPAL) • Resistant or balance training • Medicines alteration and/or titration • Behaviours Modification and Self-Maintenance awareness 7. Initiation of Orlistat if BMI > 35 and < 2% weight loss after 3 months 8. Referral for bariatric assessment if deemed suitable and after 12 months failed treatment.

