Again although weight management is an important issue in the care of people with type 2 diabetes it is not the focus of the clinic; basic advice is provided in diet and physical activity by diabetes educators. Limited state funded dietetic services are utilised in the care of paediatrics with diabetes and generally adult individuals with type 1 and some with type 2 with pre-existing co-morbidities. Individuals with weight issues who are referred to state funded dietetic services for individualisation of advice are presented with a letter indicating that they ‘are not likely to be seen so will not be placed on a wait list’ and a list of private dietitians is provided. The same issue prevails as listed above in relation to financial capacity of the individuals. Thus, the majority of people with type 2 diabetes without co-morbidities or co-morbidities that are controlled, will not have personalised calculations of energy requirements needed and specific advice on the particular caloric decreased required to provide weight loss. In addition, the reasons behind eating behaviour and weight gain are more often from a psychology basis and/or related to funding of differing food types. Another limited health professional resource in the north west.

Methodology *(continue)*

Management of Cross Contamination TSRAC QUESTION 3 (Response)

- Randomisation will be achieved by method listed above
- Cross contamination is managed by several means:
 - The clinics are run on alternate days – thus patients are unlikely to come across each other – they may within the community as they would with any other RCT
 - The interventions which include multidisciplinary assessment and care, the use of orlistat and potentially bariatric surgery if identified as a suitable candidate requires assessment and referral – the control group patients will not have the assessments performed routinely and/or be in the setting to have these referrals created
 - The intervention group utilises a different credentialled diabetes educator than the ones used in the traditional (usual care) diabetes clinic
 - The endocrinologist involved in this study will mainly be involved in the AMOS clinic – during other clinics he will be seeing patients with type 1 diabetes of lower BMI who do not meet the criteria and due to different disease process their needs will differ
 - An alternate endocrinologist not involved in AMOS will see the control group within the traditional (usual care) diabetes clinic

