- “The Australian Clinical Practice Guidelines for the Management of Overweight and Obesity in Adults” (NHMRC, 2013) provide an evidence-based, stepped approach to obesity management. The first level of management is lifestyle intervention, comprising exercise, nutrition and psychological intervention. The second level of management is medication management. The third level of management is surgery. The guidelines consider that higher levels of management are indicated when lower levels of management have been insufficient to achieve desired clinical outcomes. This is the management approach the hospital research team will adopt in their patient management strategies.
- However, the control group in this study will receive ‘usual care’. The research team is aware this means patients in the intervention or control groups may receive lifestyle, medication and / or surgical management through alternative clinical pathways (e.g. through primary care, private hospital or other sources of clinical support). This is usual in obesity clinical trials with a ‘usual care’ control arm (see the Australian Clinical Guidelines discussion on this). Consistent with other obesity studies, we will account for any differences post-hoc in our data analysis.

AMOS Research Project Participant Flow Chart

Study Duration/Timelines:

Stage 1: Recruitment of participants to study and informed consent (0 – 3 months)

Stage 2: Data collection, referral to therapies (3 – 12 months)

Stage 3: Ongoing recruitment and informed consent (6 – 9 month)

Stage 4: Initial data analysis (15 months)

Stage 5: Data Analysis and Interpretation (24-26 month)

Stage 6: Presentation and publication (15 and 26 month)

Study Population

Participants

Inclusion Criteria

- Person with BMI >30 with waist circumference \geq 88cms in women and \geq 102cms in men
- Those aged < 75 years of age
- Patient has diabetes mellitus
- Already in the care of the North West diabetes service
- Able to provide informed consent
- Not pregnant or breastfeeding

Exclusion Criteria

- Person with diabetes with a BMI > 30 with waist circumference < 88cms in women and <102cms in men
- Person with diabetes with a BMI \leq 30
- Those aged \geq 75 years of age
- Any pregnant or breastfeeding person with diabetes
- Any person with diabetes < 18 years of age
- Any person with a cognitive impairment, an intellectual disability or uncontrolled psychotic illness

Lay Description of Participation

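### The individualised HbA1c target behind a secondary responder outcome is neither recorded nor tied to baseline, so the threshold can depend on arm or on treatment

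*Protocol*

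**What the plan says.** - **Outcome.** The Outcomes section lists as secondary the "proportion of participants achieving individualised HbA1c targets according to the Australian Diabetes Society guidelines", assessed "at 12 and 24 months post baseline; also 12 months post intervention".
- **What is collected.** The outcome-measures table schedules the HbA1c value (row "HbA1c, Lipids, eGFR LFTs") at every visit. It has no row for an individual target. Demographic data and diabetes duration are taken at baseline only. Co-morbidities and medications are taken at baseline, 12 months, 24 months and 12 months post intervention.
- **Who manages each arm.** The Rationale for Study Design describes "separating participants from the control and intervention group into different clinics". Under Management of Cross Contamination, "The endocrinologist involved in this study will mainly be involved in the AMOS clinic", while "An alternate endocrinologist not involved in AMOS will see the control group within the traditional (usual care) diabetes clinic". The diabetes educators differ between the arms as well.
- **Use of a target in care.** The control column of the table of differences between the arms includes "Referral to diabetes educator as needed for ongoing education if HbA1c above target". It does not say where that target comes from or when it is set.
- **Entry.** The disease criterion is "Patient has diabetes mellitus". There is no HbA1c threshold.
- **Analysis.** Dichotomous outcomes go to logistic regression, and adjusted relative risks come from a Poisson model with robust variance. The adjustment list is age, pre-existing diabetes, socio-economic status and ethnicity.

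**The concern.** When the cut-off varies by patient, it is part of the data, and a responder comparison is only as sound as the way the cut-off was obtained. Two routes could make it depend on arm.

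1. A target taken from the clinical record would be the managing team's target, and the two arms have different teams.
2. A target derived from the guideline at follow-up would use co-morbidities and medications as they stand at that visit. The protocol collects these again in order to see how they change under obesity treatment. If the guideline's individualisation draws on them, treatment could move the threshold, even when everyone applies the guideline in good faith.

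In either case the proportions at target could differ between arms with no difference in HbA1c. The result would be read as better or worse glycaemic control when it reflects the yardstick.

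**Working it through.** **Passages side by side.** Four questions decide whether the threshold is protected.

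| Question | What the protocol states |
|---|---|
| Who derives the endpoint target? | Not stated |
| From which variables, by what rule? | A guideline is named; its inputs are not |
| At which date, and may it change? | Not stated |
| Where is it recorded? | No row in the collection table |

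That the teams know the arm is inferred from the separate clinics; the protocol does not discuss masking. No masked assessor is described for this outcome.

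**Sequence.** The Randomisation section assigns arms from a pre-numbered patient list before allocation to clinics. Each arm's pre-assessment then takes place in its own clinic. The Lay Description instead puts written consent before random placement. Neither account contains a step at which a target is set.

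**Size.** The protocol gives no figure for this outcome, so there is none to reproduce. The group size used below does reproduce: with d = 0.5, power 0.95 and two-sided alpha 0.05, n = 2 × (1.960 + 1.645)² / 0.5² ≈ 104 per arm (105 with the exact t), against 106 stated.

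Assumed inputs, none of them from the protocol:

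- HbA1c normal, SD 1.5, mean 7.5, 8.0 or 8.5%, identical in both arms
- reference threshold 7.0%, with 7.5% for a share f of one arm, f = 0.2 to 0.5 (illustrative values only)
- all 106 per arm analysed, unadjusted comparison of two proportions

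Formulas, with m the mean and Φ the standard normal distribution function:

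- p₁ = Φ((7.0 − m)/1.5)
- gap = Φ((7.5 − m)/1.5) − p₁
- false difference D = f × gap, and p₂ = p₁ + D
- SE₀ = √(2p̄(1 − p̄)/106), with p̄ the mean of p₁ and p₂
- SE₁ = √([p₁(1 − p₁) + p₂(1 − p₂)]/106)
- chance of p<0.05 = Φ((D − 1.96·SE₀)/SE₁) + Φ((−D − 1.96·SE₀)/SE₁)

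| Mean | P(≤7.0) | P(≤7.5) | Gap, points | D at f = 0.2 | D at f = 0.5 | Chance of p<0.05 at f = 0.2 | At f = 0.5 |
|---|---|---|---|---|---|---|---|
| 7.5 | 0.369 | 0.500 | 13.1 | 2.6 | 6.5 | 6.8% | 16.2% |
| 8.0 | 0.252 | 0.369 | 11.7 | 2.3 | 5.8 | 6.7% | 15.7% |
| 8.5 | 0.159 | 0.252 | 9.4 | 1.9 | 4.7 | 6.5% | 14.3% |

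Worked line for mean 7.5 and f = 0.5: p₁ = 0.369, p₂ = 0.435, D = 0.065, SE₀ and SE₁ ≈ 0.067. The chance is Φ(−0.99) + Φ(−2.94) ≈ 0.160 + 0.002 = 0.162.

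With one target rule applied without knowledge of arm, the same HbA1c distributions give an expected difference of 0 and a rejection rate near 5%.

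**Patients at target at entry.** On the same assumed distribution, 16 to 37% would already meet a 7.0% threshold at baseline. Randomisation balances them in expectation, so they can dilute the contrast but do not bias it.

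**The case against.** **The outcome refers to a guideline, not to a clinician's choice.** This is the strongest objection, and part of it stands. No passage says that the treating team sets or revises the endpoint target. The control-arm referral trigger concerns care and is not linked to the endpoint. Having different endocrinologists is a deliberate safeguard against contamination. How much discretion the guideline leaves cannot be checked from the documents. But naming a guideline fixes neither the date, nor the assessor, nor which visit's data feed it, and the second route above needs no discretion at all.

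**The derivation rule may be in the analysis plan.** A plan not shown here could apply an algorithm to baseline data. That limits the point to what the protocol fixes: an outcome with a patient-specific threshold, a collection schedule without it, and an adjustment list without baseline glycaemic status.

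**Stronger readings that the documents do not support.**

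- A reader might infer that the outcome favours AMOS. The direction is unknown; a stricter AMOS team would push the result the other way.
- A reader might infer a large false-positive risk. Making every patient in one arm 0.5 points looser, with SD 1.0 to 2.0, gives 8.2 to 19.1 points and a 27 to 82% chance of p<0.05. Nothing in the protocol suggests a shift of a whole arm.
- A reader might see patients already at target as a source of bias. They are not, and keeping or losing target over 24 months is itself informative.

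**Conclusion.** The point holds as a weakness in how a secondary outcome is fixed. The threshold can depend on arm or on treatment, and nothing in the protocol prevents this; nothing shows that it will happen. The size, about 2 to 6.5 percentage points with a false-positive chance of about 6.5 to 16% against a nominal 5%, rests wholly on the assumed HbA1c distribution, target gap and share affected. The continuous HbA1c primary outcome uses no target and is untouched, so it also offers a check: a responder difference without a matching difference in mean HbA1c should prompt a look at the targets.

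**What to change.** For the endpoint only:

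1. Derive each participant's target once, from baseline data (age, diabetes duration, co-morbidities, medications), by applying the cited guideline through one written rule to both arms.
2. Have this done by someone working from a de-identified extract with the arm removed. Deriving it before the arm is known to anyone would not fit allocation from the patient list, which precedes the clinic baseline; removing the arm from the extract does fit. The protocol's existing de-identified sheet is not described as masked to arm, so this must be stated.
3. Restrict the inputs to items ascertained in the same way in both arms, because the AMOS clinic screens more widely from its first visit.
4. Use that target at 12 months, 24 months and 12 months post intervention.
5. Add at-target status at baseline, or baseline HbA1c, to the logistic and Poisson models for this outcome. This is for precision, not to remove bias.

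Targets used in care stay with the clinicians, and no target value is proposed here. The cost is one derived field per participant from data already scheduled, and a short written rule. The downside is that the endpoint target may differ from the one later used in care.
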